**STUDY PROTOCOL AND STATISTICAL ANALYSIS PLAN**

## 1. Methods

### 1.1. Study design

This will be a multisite randomized active-comparator controlled clinical trial. Due to the nature of the intervention, subjects and investigators will not be able to be masked to the intervention. The assessor will not be able to be masked to group assignments, as the presence or absence of certain variables in the dataset, namely the perturbation level, will immediately reveal group assignment.

**Sample Size Estimation and Study Timeline:** Using the pilot data, a Cohen's d effect size of 0.39 was calculated and a two-tailed power analysis ( $\alpha=0.05$ ) was conducted. For the observed effect size, an estimated sample size of 214 participants would achieve 80% power. Using this estimate, and the estimates of the participating sites of the number of potential subjects that could be recruited, enrollment is expected to last 12-18 months (Table 1).

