BWSS (Aretech LLC, Ashburn, VA) and the Training Responses in Postural Rehabilitation (TRiP) balance perturbation module (Aretech LLC, Ashburn, VA) will be the primary pieces of equipment required to complete this study. All study locations already have the ZeroG BWSS and TRiP module installed.

In addition to the equipment, several outcome measurements will be collected throughout the study duration. Balance specific measurements that will be collected include the BBS, an objective balance measure, and the Activities Specific Balance (ABC) scale, a subjective patient reported measure. When appropriate for the patient, an admission BBS is collected within 72 hours of admission at all study locations by the patient's primary therapist. This admission evaluation will be used to initially identify potential subjects with an admitting BBS of 21 or greater; this will be used as the pre-intervention assessment (pre-assessment) during data analysis. When patients are discharged, a follow-up BBS is typically collected at all study locations. However, discharge may not always occur in a timely fashion after the conclusion of the study. To address this, a post-intervention assessment (post-assessment) will be collected within 48 hours of the last study session if not already collected by the participant's primary therapist during that time. The patient reported ABC scale will be collected during the informed consent process and immediately following the last study session.

To evaluate gait, the objective self selected 10 Meter Walk Test (10MWT) assessment will be conducted. If not already conducted during the participant's admission evaluation, a 10MWT pre-assessment will be conducted by site investigators within 48 hours prior to the first study session. A post-assessment 10MWT will be collected within 48 hours of the last study session if not already collected by the participant's primary therapist during that time.

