**BWSS-P Intervention Group:** The BWSS-P intervention group will also conduct 2 to 6 study sessions over a two-week period. Each session must have an active time of at least 15 minutes in the system, up to 30 minutes for each session. Participants in the BWSS-P group will conduct the same balance and gait exercises as the control group, however, these sessions will include eight perturbations, two in each direction (lateral left, lateral right, anterior, and posterior). Perturbations will occur while static/standing (lateral, anterior, posterior) and dynamically while ambulating (anterior, posterior). Each of the 2 to 6 study sessions will be part of the subject's normal course of therapy. As this is an active clinical comparison, clinical parameters and progression, other than those described above, will be determined by the treating therapist (i.e. percent body weight support and use of assistive devices) to ensure success and appropriate challenge to the subject. The TRiP or perturbation level will be progressed to the point of loss of balance, or very near loss, without recovery. The perturbation level should then be then decreased by one level for treatment. All 8 perturbations will occur at this level until it is clinically appropriate to progress again. The intensity of TRiP perturbation ranges from level 1 to 10, minimal to maximum, respectively.

**Post-Assessments:** After the completion of the subjects' final BWSS session before discharge, investigators will conduct an ABC and 10MWT post-assessment no longer than 48 hours following the final session. Follow-up BBS are often completed prior to discharge as part of patient/participant's standard of care. However, in the case that there is an unexpected delay or there is a significant length of time until the participant's discharge, a post-assessment BBS will be conducted no longer than 48 hours following the last session.

**Data Analysis:** Data were analyzed using GraphPad Prism (version 10; GraphPad Software, Boston, MA) and RStudio (version 4.2.2, Posit Software, PBC, Boston, MA] using the *car* package.

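### The one reason given for an unmasked assessor concerns a dataset column, so it justifies neither an unmasked outcome rater nor an analyst who sees the arm

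*Combined protocol and SAP*

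**What the plan says.** Section 1.1 states that "subjects and investigators will not be able to be masked to the intervention". It then turns to the assessor: "The assessor will not be able to be masked to group assignments, as the presence or absence of certain variables in the dataset". The same sentence goes on to identify the variable it has in mind: "namely the perturbation level, will immediately reveal group assignment". The word assessor is not defined there or elsewhere.

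On who measures the outcomes:

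- **BBS, baseline.** Under Equipment and Instruments, "an admission BBS is collected within 72 hours of admission at all study locations by the patient's primary therapist". This is before consent and assignment.
- **BBS, post-intervention.** The same section says it "will be collected within 48 hours of the last study session if not already collected by the participant's primary therapist during that time". If the primary therapist has not done it, no rater is named.
- **10MWT, baseline.** If it was not done at admission, "a 10MWT pre-assessment will be conducted by site investigators within 48 hours prior to the first study session".
- **10MWT, post-intervention.** Equipment and Instruments uses the same wording as for the BBS, so the primary therapist's result may be used. The Post-Assessments paragraph says instead that "investigators will conduct an ABC and 10MWT post-assessment no longer than 48 hours following the final session".
- **ABC.** It is patient-reported.
- **GG0130 and GG0170.** Data Analysis lists both among the primary outcomes, with the BBS, ABC and 10MWT. The plan does not say who scores them.

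Data Analysis leaves the choice between t-test and Mann-Whitney, and among multiple-comparison procedures, to the analyst. It names no ANCOVA covariates.

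**The concern.** The BBS depends on an observer's judgement, and the 10MWT can be influenced by encouragement. Participants already know their arm. A rater who also knows it can add a systematic difference between arms that cannot afterwards be separated from a treatment effect. Because the admission BBS precedes assignment, such a difference would enter only the post score, so taking change from baseline would not remove it.

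An analyst who sees the arm while choosing tests and covariates is a second, separate exposure. The only argument in the plan for accepting either one is the perturbation-level column, so it matters whether that argument holds.

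**Working it through.** **Step 1. What the perturbation level is.** It is a treatment setting, adjusted and recorded during BWSS-P sessions: "The TRiP or perturbation level will be progressed to the point of loss of balance, or very near loss, without recovery". Table 2 lists it as a session recording, separate from the outcome assessments.

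**Step 2. Test the reason under each meaning of assessor.**

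| Meaning | Does the column reveal the arm to this person? | Is the column needed for the task? | What follows |
|---|---|---|---|
| Outcome rater | Only if the rater is shown the session records | No | The reason does not apply |
| Data analyst | Yes, if it is in the file | No analysis listed in Data Analysis uses it. It does not exist for controls, so it cannot be a covariate in a between-arm model | The obstacle can be removed, and rater masking is not addressed |

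**Step 3. Look for protection elsewhere.** No section requires that the post-intervention rater did not treat the participant or does not know the arm. The non-treating co-investigators described under Subject assignment hold the assignment lists, so they are not masked. No section provides for coded arms or a restricted analysis file.

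**Step 4. Reproduce the plan's sample size.** The inputs from section 1.1 are d = 0.39, two-sided α = 0.05, 80% power and a total of 214. Allocation is equal (Subject assignment).

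- Normal approximation: n per arm = 2(1.960 + 0.842)² / 0.39² ≈ 103.2, rounded up to 104, total 208.
- Two-sample t-test: 104.18, rounded up to 105, total 210.
- An unrounded d of 0.385 to 0.386 gives exactly 214 by t-test.
- Power at 107 per arm and d = 0.39 is 0.810 by t-test.

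The stated 214 is therefore reproduced to within rounding of d, and this point does not change it.

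**Step 5. Illustrate the size of a rating bias.** Let b be a systematic difference in SD units favouring one arm, with no true effect. The documents give no value for b, so it is an assumption. The shift of the test statistic is b × √(107/2) = 7.314b, and P(p<0.05) ≈ Φ(7.314b − 1.96) + Φ(−7.314b − 1.96).

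| b (SD) | Shift | P(p<0.05), normal | P(p<0.05), noncentral t | b / 0.39 |
|---|---|---|---|---|
| 0 | 0 | 0.050 | 0.050 | 0% |
| 0.05 | 0.366 | 0.0655 | 0.0653 | 13% |
| 0.10 | 0.731 | 0.1132 | 0.1126 | 26% |
| 0.20 | 1.463 | 0.3099 | 0.3075 | 51% |

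These figures are for one outcome tested once. They say nothing about the effect of an unmasked analyst, which was not quantified.

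**The case against.** **The sentence may simply be about the analyst.** It speaks of variables in a dataset, and on that reading it is coherent. A reader might infer that the plan mistakes the rater for the dataset. With the term undefined, the text does not establish that. The objection stands, but it moves the gap rather than closing it, because rater masking is then left without any statement.

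**A masked rater is not free.** Investigators are declared unmasked, co-investigators hold the lists, and sessions form part of normal care, so other therapists may know the arm. The documents give no staffing figures. A reader might infer that the exposure could be removed at no cost. Only the data-handling step is close to that, and a guaranteed masked rater could need extra resources.

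**The treating therapist is not named as rater.** A reader might infer that the person who delivered the sessions scores the outcome. The plan names the primary therapist and never says that this person delivers the study sessions. What stands is that nothing excludes it.

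**Reach is limited.** Rater masking cannot protect the self-reported ABC. The timed 10MWT leaves less room for judgement than the BBS, and the raters of the two GG scores are unknown. Both arms do the same balance and gait exercises, which may narrow any difference in expectation. All of this stands.

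**Coding the arms does not stop selection among tests.** An analyst with A/B labels still sees p-values. This also stands. Coding hides which arm a choice favours, and it helps only alongside models fixed in advance.

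**Conclusion.** The point holds in limited form. The stated reason does not justify an unmasked rater, and it describes an avoidable obstacle to a masked analyst. This is so whichever meaning of assessor was intended. The exposure lies mainly in the post-intervention BBS, less in the post-intervention 10MWT, and in the analyst's open choices.

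The size is unknown. The rise from 5% to about 6.5%, 11% or 31% rests on assumed biases of 0.05, 0.10 and 0.20 SD, on 107 analysed per arm and on a single test. Zero bias is also compatible with the documents. A reader might infer from the larger figures that the trial's result would be materially biased, but nothing in the plan shows that. This warrants a correction to the wording and data handling. It is not a reason to change the sample size.

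**What to change.** 1. Delete the rationale in section 1.1, define assessor, and treat the outcome rater and the analyst separately.
2. At transfer to the Lead Site, keep the perturbation level in a separate file. Give the analyst arms coded A and B until the between-arm models (choice of test and covariates) are fixed, preferably before the first interim analysis in Table 1. Keep on/off-time, or a valid-session count derived from it, in the analysis file. The 15-minute active-time rule for counting a session depends on it, and the plan does not say that it reveals the arm. This step assumes the analyst does not hold the assignment lists, which the plan should state.
3. Where existing staffing allows, have the post-intervention BBS and 10MWT done by a therapist who neither delivered that participant's study sessions nor holds the list. In every case record who rated and whether they knew the arm, and use this in a sensitivity analysis. Reconcile the two statements on who does the post-intervention 10MWT.
4. State that the ABC stays unmasked because it is self-reported, and state who scores GG0130 and GG0170.

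The cost is revised wording, one extra export step and some scheduling effort. Masking will be incomplete. Data Analysis is written in the past tense. If data collection has ended, step 3 reduces to reporting who rated and whether they knew the arm, as far as this can be established.

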**Table 1. General Timeline**

Year 1	Month											
	1	2	3	4	5	6	7	8	9	10	11	12
Clinical Trial Registration 	X											
Purchasing 	X											
Staff Training/Check-in	X			X					X			
Steering Committee meeting	X	X	X	X	X	X	X	X		X	X	X
Enrollment Target 		12	12	12	12	12	12	12	12	12	12	12
Completion Target 			12	12	12	12	12	12	12	12	12	12
Interim data analysis (25% and 50% recruitment)							X				X	
Year 2	Month											
	13	14	15	16	17	18	19	20	21	22	23	24
Staff Training/Check-in	X											
Steering Committee meeting	X	X	X	X	X	X	X	X	X	X	X	X
Enrollment Target 	12	12	12	12	12	12	12					
Completion Target 	12	12	12	12	12	12	12	12				
Data analysis									X	X		
Manuscript preparation; Poster abstract submission										X	X	X
Clinical Trial Registration: Data updates 										X	X	

This study will be registered and maintained at clinicaltrials.gov; Registration will be completed prior to recruiting the first subject.

If grant funding is able to be attained, purchasing outlined in the grant will be completed in month 1 of the award period.

Enrollment and completion targets are estimates based on an 18 month enrollment period. For a 12 month enrollment period, the enrollment and completion targets would be 18 participants per month, with the completion target ending in month 13.

**Participants, Settings, and Inclusion/Exclusion Criteria:** To participate in this study, participants must be recruited at one of the three participating rehabilitation centers: Gaylord Specialty Healthcare (Wallingford, CT), MedStar National Rehabilitation Hospital (Washington, DC), or Spaulding Rehabilitation Hospital Cape Cod (Sandwich, MA).

To be eligible for study participation, subjects must meet the following *Inclusion Criteria*:

- Admitted to one of the listed study locations for inpatient rehabilitation following either

ischemic or hemorrhagic stroke and medically stable for the therapy program.

- Be 18 years of age or older.
- Discharge date of 10 days or longer at study consent
- Have at least a moderate fall risk or better, shown by an admission BBS score of 21/56 or greater.
  - Patients that score below 21 or are non-ambulatory will not be considered for this study.
  - Patients that are emergently re-admitted to acute care and subsequently re-admitted to the stroke rehabilitation program will be reassessed for appropriateness of continuation in the study on a case by case basis.
  - Patients that progress to a BBS score of 21 or greater during their stay, and have a set discharge date of 10 days or longer, can be approached for study recruitment.
- Appropriate cognition
  - Able to read and understand the consent, in English or a language available by translator services, based on the judgment of the clinical team, either by using outcomes measures, i.e. SLUMS  $\geq$  20, or through clinical evaluations and team discussion. Eligibility will ultimately be decided by the treating physician and/or in combination with the participant's clinical team.
- Ability to tolerate and actively participate in at least 2 and up to 6 study related BWSS therapy sessions.
  - Study related therapy sessions will last a minimum of 15 minutes, up to 30 minutes in the BWSSs.

Those who present with one or more of the following *Exclusion Criteria* will not be eligible for study participation:

- Cognitive deficits that would disrupt the ability to provide informed consent as described above
- Active enteric infection control precautions
  - Subjects would be eligible once precautions are lifted
- Ongoing orthostasis
- Uncontrolled hyper/hypotension
- Active seizures
- Spinal stabilization with the use of Halos
- Unstable skin structures (i.e. skin grafts)
- Chest tubes
- Unstable rib or lower extremity fractures
- Severe osteoporosis
- Subjects where pressure around the abdomen, thighs, groin, or shoulders is contraindicated
- New limb amputations
- Vestibular disorders that may impact balance
- Premorbid conditions that may impact balance
- Patients requiring more than 50% high flow oxygen as consistent with inpatient therapy guidelines
- Subjects who weigh more than 450 pounds, per the structural limitations of the ZeroG system
- Anyone belonging to a vulnerable population as described below, including subjects under the age of 18 and who are or might be pregnant

Equipment and Instruments: Several pieces of equipment and outcome instruments will be needed for this study. The ceiling-track mounted, FDA listed, ZeroG body weight support system

BWSS (Aretech LLC, Ashburn, VA) and the Training Responses in Postural Rehabilitation (TRiP) balance perturbation module (Aretech LLC, Ashburn, VA) will be the primary pieces of equipment required to complete this study. All study locations already have the ZeroG BWSS and TRiP module installed.

In addition to the equipment, several outcome measurements will be collected throughout the study duration. Balance specific measurements that will be collected include the BBS, an objective balance measure, and the Activities Specific Balance (ABC) scale, a subjective patient reported measure. When appropriate for the patient, an admission BBS is collected within 72 hours of admission at all study locations by the patient's primary therapist. This admission evaluation will be used to initially identify potential subjects with an admitting BBS of 21 or greater; this will be used as the pre-intervention assessment (pre-assessment) during data analysis. When patients are discharged, a follow-up BBS is typically collected at all study locations. However, discharge may not always occur in a timely fashion after the conclusion of the study. To address this, a post-intervention assessment (post-assessment) will be collected within 48 hours of the last study session if not already collected by the participant's primary therapist during that time. The patient reported ABC scale will be collected during the informed consent process and immediately following the last study session.

To evaluate gait, the objective self selected 10 Meter Walk Test (10MWT) assessment will be conducted. If not already conducted during the participant's admission evaluation, a 10MWT pre-assessment will be conducted by site investigators within 48 hours prior to the first study session. A post-assessment 10MWT will be collected within 48 hours of the last study session if not already collected by the participant's primary therapist during that time.

**Subject identification, recruitment, and pre-assessments:** As described above, qualifying patients will initially be screened/identified through internal reports generated at each study site summarizing admission BBS scores for recently admitted patients. Screening will continue until the target number of participants have completed the study and/or the pre-determined statistical guidelines have been met. After initial screening, the additional inclusion/exclusion criteria will be considered with attending physician approval and the patient approached for consent. After collecting informed consent, participants will be asked to complete an ABC scale pre-assessment. If it was not already conducted by the participant's primary physical therapist at admission, a 10MWT pre-assessment will be conducted within the 48 hours prior to the first treatment session. The admission BBS score will be counted as the participants' BBS pre-assessment. Study procedures and assessments will be conducted according to the general timeline shown in **Table 2**.

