**Table 2. Schedule of Study Procedures and Assessments**

Procedure	Admission	Screening	Pre- Intervention	Treatment Sessions						Post- Intervention
				1	2	3	4	5	6	
BBS	X									X
Report generation	X									
Informed consent		X								
Participant group assignment			X							
Collection of demographic and other secondary information as described below 				X						X
Additional stroke information 				X						X
ABC scale				X						X
10MWT				X						X
BWSS Control Intervention					X	X	X	X	X	X
BWSS-P Intervention					X	X	X	X	X	X
TRiP/Perturbation level recording					X	X	X	X	X	X
System on-time/off-time recording					X	X	X	X	X	X
Data transfer										X

The described information can be collected, as available, any time after the subject has consented to the study, but before de-identified data is transferred to the Lead Site.

**Subject assignment:** Consented subjects will be assigned to either the BWSS Standard Intervention (Control) Group or BWSS with Balance Perturbations (BWSS-P) Intervention Group according to a pre-generated randomized assignment sheet. Each randomized assignment sheet will consist of equal BWSS Control and equal BWSS-P assignments whose order has been randomized using the random list generator at <https://www.random.org/lists/>. Co-Investigators at each site, who will not be delivering the study interventions directly, will be given a unique list with a number of assignments that is in proportion to the number of subjects expected to be recruited at the site; additional assignment lists will be generated if needed. These co-Investigators will be responsible for communicating group assignments to study therapists delivering the intervention, and for ensuring that randomization and treatment order is maintained. It is expected that if the assignment scheme is not maintained for whatever reason, that they will report the incident to the steering committee, described below, and how it was/or still needs to be rectified. No matter group assignment, all consented subjects will be asked to conduct all pre- and post-assessments.

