Descriptive data is reported as mean (95% confidence interval). If hypothesis testing was done, data were reported with a p-value, and significance was set at  $\alpha=.05$ . The primary outcome measures used in our analyses were the BBS, ABC, 10MWT, CMS GG0130 Mobility scores, and CMS GG0170 Self-care scores. Data were determined to be missing completely at random and were dealt with via complete case analysis and mixed-effects analysis as applicable. Data were also assessed for violations in assumptions of their given tests, and were dealt with via non-parametric analysis as necessary.

Categorical data was analyzed using Chi-square testing. Unpaired t-tests or Mann-Whitney U tests were utilized as necessary to evaluate between-group differences in continuous outcome variables.

Analysis of covariance (ANCOVA) was used to account for between group differences while controlling for covariates. To evaluate if there were differences between pre- and post-intervention data, a 2-way analysis of variance (ANOVA) was utilized, with mixed-effects analysis being utilized when data was missing. Differences in average improvement by number of sessions completed were evaluated using a 2-way ANOVA. Differences in outcome measure between testing sites were analyzed using one-way ANOVA or Kruskal-Wallis testing. Multiple comparisons were analyzed using, Fisher's, Dunn's, Tukey's multiple comparison tests as appropriate.

References:

2. Parametric ANCOVA and the Rank Transform ANCOVA When the Data are Conditionally Non-Normal and Heteroscedastic - Stephen F. Olejnik, James Algina, 1984 [Internet]. [cited 2024 Apr 4]. Available from: <https://journals.sagepub.com/doi/10.3102/10769986009002129>

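### Interims at 25% and 50% and undefined statistical guidelines that can end screening sit beside an unadjusted final .05; if they permit an efficacy stop, type I error exceeds 5%

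*Combined protocol and SAP*

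**What the plan says.** Table 1 has a row labelled "Interim data analysis (25% and 50% recruitment", marked in months 7 and 11. Its footnote 3 adds that "Enrollment and completion targets are estimates based on an 18 month enrollment period".

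The section on subject identification, recruitment and pre-assessments gives the rule for ending recruitment: "Screening will continue until the target number of participants have completed the study and/or the pre-determined statistical guidelines have been met". The guidelines stand beside the target number as a further way to end screening. No supplied section says what they are.

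Section 1.1 bases the sample size on d=0.39 and a two-tailed test at .05: "For the observed effect size, an estimated sample size of 214 participants would achieve 80% power". It makes no allowance for interim looks.

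The Data Analysis section does not mention the interims. It says that "data were reported with a p-value, and significance was set at" .05. It names several primary outcomes ("The primary outcome measures used in our analyses were the BBS, ABC, 10MWT" and two CMS scores) without saying which of them an interim would examine.

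**The concern.** Two scheduled looks, a statistical criterion that can close recruitment, and a final test at the full .05 do not fit together if the criterion is an efficacy rule. Any chance of declaring a difference at an interim is then added to a final test that already uses the whole 5%. The plan's only stated significance level is .05. Someone applying it literally at each look would more than double the nominal error if stopping is allowed in either direction.

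The second consequence is estimation. A trial that stops early because the difference is large reports, on average, too large a difference.

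Without the missing rule, a reader cannot tell whether the trial's type I error is 5% or more.

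**Working it through.** **Inputs.** d=0.39, two-sided .05, N=214 and 80% power (section 1.1); equal allocation (Subject assignment); looks at 25% and 50% (Table 1); final level .05 (Data Analysis). The interim thresholds are assumed, because none is given. The calculation covers one endpoint and a normal approximation, with no binding futility stop.

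**1. The plan's sample size.** n per arm = 2(1.960+0.842)²/0.39² = 103.2, so 104 per arm and 208 in total. The t-based version gives 105 per arm, 210 in total. An unrounded d of about 0.385 gives 214. The figure is therefore reproduced as a fixed, single-look design. At N=214 the drift is 0.39×√(214/4) = 2.853, and power is Φ(2.853−1.960) = 81.4%.

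**2. Overall type I error with a final test at .05.** At information 0.25, 0.5 and 1, the statistics Z1, Z2 and Z3 are jointly normal with correlation √(tj/tk): 0.707 between looks 1 and 2, 0.5 between 1 and 3, and 0.707 between 2 and 3. Let c be the interim critical value.

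- Stopping in either direction: error = 1 − P(|Z1|<c, |Z2|<c, |Z3|<1.960).
- Stopping only in favour of BWSS-P: error = 1 − P(Z1<c, Z2<c, |Z3|<1.960).

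| Interim two-sided p | c | Either direction | Favouring BWSS-P only |
|---|---|---|---|
| <.001 | 3.291 | 5.08% | 5.04% |
| <.005 | 2.807 | 5.49% | 5.25% |
| <.01 | 2.576 | 6.08% | 5.54% |
| <.05 | 1.960 | 11.35% | 8.17% |

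Descriptive interims leave the error at 5.0%, and futility-only interims leave it at 5.0% or less.

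**3. Sensitivity to timing.** At 12 completions a month from month 3, Table 1 implies 5×12 = 60 completers by month 7 and 9×12 = 108 by month 11. These are 28% and 50% of 214. For p<.001, p<.01 and p<.05 the errors become 5.07%, 6.03% and 11.13% (either direction), or 5.04%, 5.52% and 8.07% (favouring BWSS-P only). Timing hardly matters; the threshold and the direction do.

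**4. Estimate after an early stop, if the true d is 0.39.** At 25% (N=53.5) the standard error of d is √(4/53.5) = 0.273. A stop at p<.01 therefore needs an observed d above 2.576×0.273 = 0.70.

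| Interim p | Chance of a stop at 25% | Mean estimate at that stop |
|---|---|---|
| <.001 | 3% | 1.0 |
| <.01 | 13% | 0.84 |
| <.05 | 30% | 0.71 |

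**5. A boundary that holds 5%.** The Lan-DeMets O'Brien-Fleming spending function at .025 per side spends 2[1−Φ(2.2414/√t)] per side. Doubled, this is .0000147 by 25%, .00305 by 50% and .05 at the end. The critical values are 4.333, 2.963 and 1.969. With two-sided levels .000015, .0030 and .0490, overall error is 4.998% and power at d=0.39 is 81.3%. At 60 and 108 of 214 the levels are .000046, .0032 and .0489.

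**The case against.** The strongest reply is that no document figure supports any particular error rate. The guidelines could be a futility rule, a sample-size check or simply the enrolment target, and under each of these there is no inflation. They are called pre-determined, so they may be written down elsewhere. The Subject assignment section says of departures from the assignment scheme that "they will report the incident to the steering committee, described below", and that description is not in the supplied text. The Data Analysis section reports no interim comparison or early stop. All of this stands, and it is why the error rates are conditional.

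Direction is also a fair objection. The 11.3% counts stops in favour of either arm. If only results favouring BWSS-P can stop the trial, the figure at p<.05 is 8.2%, and with a strict p<.001 rule the inflation is negligible.

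A reader might draw three stronger conclusions that the documents do not support:

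- **That the trial runs at 11.3%.** This needs p<.05 at both looks, stopping in either direction and no binding futility rule, none of which is stated.
- **That an efficacy look has already taken place.** The past tense ("Data were analyzed using GraphPad Prism") raises the question but does not answer it.
- **That a futility rule could not absorb the inflation.** That depends on the rule: a binding stop at |z|<1.25 at 50%, for example, brings p<.01 down to 4.6%.

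What the objection does not remove is the gap itself. The clause treats the guidelines as a route to ending recruitment apart from the target, and the only significance level given makes no allowance for that.

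**Conclusion.** The point holds as a conditional one. The supplied plan schedules two interims, lets undefined statistical guidelines end screening, and assigns the whole two-sided .05 to the final test of a design sized for one look. If the guidelines permit an efficacy stop on one endpoint, 5% is not maintained. The excess runs from under 0.1 point (p<.001) to 6.3 points (p<.05, either direction) or 3.2 points (p<.05, favouring BWSS-P only).

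The interim thresholds are assumed. The figures also rest on a single endpoint, so the multiplicity from several primary outcomes is a separate matter and is not counted. That the guidelines are an efficacy rule is an inference. The omission of the rule from the supplied text is not. The plan should be corrected, because the remedy is cheap and the error rate cannot be determined without it.

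**What to change.** First state, in the recruitment and Data Analysis sections, whether a between-arm interim test has been done, on which endpoint, at what threshold, in which direction, and whether it could stop the trial. If the guidelines exist in another document, cite them and carry their final level into Data Analysis. Then adopt one of the following.

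- **No efficacy stopping.** Say that the interims cannot stop the trial for efficacy, and delete the guidelines clause or define it. The final level stays .05. If they are descriptive, this is wording only. If a non-binding futility rule is intended, report its power cost. As illustrations, not proposals, stopping at 50% when z<0 takes power from 81.4% to 81.1%, and stopping when z<0.5 takes it to 79.7%.
- **Efficacy stopping.** Name one endpoint, chosen by the sponsor, and use a Lan-DeMets O'Brien-Fleming boundary: two-sided p<.000015 at 25%, p<.0030 at 50% and p<.0490 at the end, recomputed at the actual information fractions. Power is about 81.3% against 81.4%. This counts as prespecified only if no between-arm interim result has been seen.

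If an efficacy interim test has already been done, disclose its threshold and direction and derive the final level from them. For stopping **in either direction**, with the same threshold at both looks:

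| Interim p | Final level | Power at d=0.39 |
|---|---|---|
| <.001 | .0492 | 81.3% |
| <.005 | .0448 | 80.5% |
| <.01 | .0383 | 79.1% |
| <.022 | .0184 | 72.6% |

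Also for stopping in either direction, above about p<.029 at both looks the interims alone spend more than 5% (8.3% at p<.05). No final level then restores it, and the report should say so. Stopping in one direction needs its own calculation.

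In every case where an efficacy stop is possible, state that the estimate after an early stop is biased upward. No option needs extra patients.
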